7.9.1.2.3 Rationale for Performance Criteria

For return to work, if the null hypothesis is rejected, it demonstrates that the distribution of times to return to work with the VenaSeal™ system is significantly different from the treatment with ETA or surgical stripping. When the P-value is less than the pre-specified alpha per adjustment of multiple comparison (described in Section 7.5) and the mean/median time of return to work in treatment of VenaSeal™ is less than that in control of ETA or Surgical Stripping, the superiority of treatment of VenaSeal™ on return to work can be declared.

The closure rate hypothesis is a non-inferiority test. The null hypothesis H_0 will be rejected when the one-sided P-value is less than the pre-specified alpha per adjustment of multiple comparison (described in Section 7.5) and the non-inferiority of treatment with VenaSeal™ on closure rate at 6 months can be declared. Further, if non-inferiority is met a test for superiority will then be conducted.

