There was one report of death (due to liver cancer) in a VenaSeal™ system subject. The liver cancer death at Day 1098 post-procedure was assessed as unrelated to the study device or study procedure. There was one report of deep venous thrombosis (DVT) in the non-index limb in an RFA subject. There were no reports of Pulmonary Embolism (PE), no reports of allergic reactions to the VenaSeal™ adhesive (cyanoacrylate), and no reports of Unanticipated Adverse Device Effects (UADEs).

VeClose Five-Year Follow-up Extension Study

The VeClose Five-Year Follow-up Extension study was conducted to gain additional follow-up data from the patients enrolled in the VeClose IDE pivotal study described above. Patients treated in both the experimental and control study arms as well as in the roll-in cohort were assessed for a 60-month follow-up visit. The study was conducted under a separate protocol and no further intervention occurred under this protocol. A total of 89 subjects completed the 60-month visit, 9 subjects were from the roll-in cohort and 80 subjects from randomization cohort (47 subjects in VenaSeal™ system and 33 subjects in RFA). 53 subjects treated with the VenaSeal™ system (subjects enrolled in VenaSeal™ system + roll-in subjects) maintained a closure rate of 94.6% at 60 months. The closure rate for 33 subjects treated with RFA was 100%. Kaplan-Meier freedom-from-recanalization analysis demonstrated non-inferiority of the VenaSeal™ system compared to the RFA group at a significance level of 0.025 (non-inferiority based on one-sided 97.5% confidence interval with lower limit = -3.5%, and margin of -10%), through the 60-month follow-up period (91.4% vs. 85.2%, respectively). These rates remained unchanged from the 36-month follow-up visit, indicating that no new GSV failures occurred between the 36- and 60-month visits in either group. No SAE, PE, DVT or treatment limb AEs were reported in both the VenaSeal™ system cohort and the RFA cohort between 36-month and 60-month follow-up.³⁰

WAVES

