6.1 Randomized Studies

Analyses will be performed on all patients who pass the point of enrollment (randomization), as according to the intention-to-treat (ITT) principle. Patients will be analyzed in the arm they are randomized to regardless of the treatment received.

There are three primary endpoints and two key secondary endpoints with formal hypothesis testing for the Randomized Studies. Multiplicity adjustment needs to be considered to control the overall type I error. Each randomized study will have a family-wise type I error rate of 0.05. Within each study, Hochberg procedure will be used to control the family-wise type I error rate to 0.05 for the primary endpoints (Benjamini & Hochberg, 1995)¹. Type I error preserved from the primary endpoints will be used for the key secondary endpoints.

A type I error of 0.0167 will be used in the following sample size calculations for this purpose.

In the two Randomized Studies, three primary endpoints will be assessed:

- 1) Peri-procedural patient satisfaction as measured by a validated patient-centered venous treatment satisfaction questionnaire (VenousTSQe) at 30 days;
- 2) Patient satisfaction as measured by a validated patient-centered venous treatment satisfaction questionnaire (VenousTSQs) at 30 days, and
- 3) elimination of clinically relevant superficial truncal disease in each target vein at index procedure. The two key secondary endpoints include achieving the anatomical closure of primary target superficial truncal veins at 6 months and the time to return to work post-index procedure.

For VenaSeal vs Surgical Stripping Study, 108 subjects randomized before 22-Feb- 2022 will be included in the analysis. These subjects will be followed for 12 months after index procedure. Since the enrollment was stopped for the VenaSeal vs. Surgical Stripping Study with up to 108 subjects, there is still reasonable power for the two TSQs and key secondary objectives. Therefore, the VenaSeal vs. Surgical Stripping Study will test two primary endpoints (Venous TSQe and TSQs at 30 days) and the key secondary endpoints. The elimination of truncal reflux at the index procedure will be summarized but not tested for hypothesis testing.

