Table 3 shows an overview of the weighted average closure rates at 6 months that were used to calculate the sample size for this endpoint.

Table 3: Weighted Average Closure Rate

Comparator	Total number of considered studies	Total sample size in considered studies	Weighted average closure rate at 6M
VenaSeal™	5	343	95.0%
ETA	18	1948	95.4%
Surgical stripping	2	320	84.8%

The null hypothesis on this key secondary endpoint is that the closure rate at 6 months in the VenaSeal™ system arm will have less than or equal to that in the control (ETA or surgical stripping) arm minus a clinically relevant difference of 10%. The alternative hypothesis is that the closure rate at 6 months in the VenaSeal™ system arm will be greater than that in the control arm minus a clinically relevant difference of 10%. Rejection of the null hypothesis will signify that the treatment with the VenaSeal™ system is not inferior to the treatment with ETA or surgical stripping.

Specifically, the null (H_0) and alternative (H_a) hypotheses are:

$$H_0: \pi_A \leq \pi_C - 10\%$$

$$H_a: \pi_A > \pi_C - 10\%$$

Where π_A and π_C are the closure rate at 6 months in the VenaSeal™ system arm and the ETA or surgical stripping arm.

The parameter assumptions are:

- $\pi_A = 95\%$ in the VenaSeal™ system arm and $\pi_C = 95.4\%$ and 84.8% in ETA and surgical stripping arm, respectively
- Likelihood Score (Farrington & Manning) test with one sided $\alpha = 0.0167$
- 1:1 randomization
- 10% attrition rate

With these assumptions, a total of 264 subjects (238 evaluable, 119 in each arm) will yield 80% power to reject the null hypothesis in favor of the alternative hypothesis of non-inferiority to the ETA arm. A total of 98 subjects (88 evaluable, 44 in each arm) will yield 80% power to reject the null hypothesis in favor of the alternative hypothesis of non-inferiority to the surgical stripping arm.

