7.5 Adjustments for Multiple Comparisons

In the randomized studies, Hochberg procedure will be used in the adjustments for multiple comparisons on primary and key secondary endpoints (Benjamini & Hochberg, 1995)¹. Familywise type I error 0.05 will be used for the primary endpoints and type I error preserved from the primary endpoints will be used for the key secondary endpoints.

VenaSeal vs. ETA Randomized Study

In each randomized study, p-values for the primary endpoints will be ordered from largest to smallest as $p_{p1} > p_{p2} > p_{p3}$ from the 3 hypothesis tests H_{p1}, H_{p2} and H_{p3} , and for the key secondary objectives in descending order as $p_{s1} > p_{s2}$ from the 2 hypothesis tests for key secondary endpoints H_{s1} and H_{s2} , the procedure is as follows:

Step 1. If $p_{p1} < \alpha$, then claim success on all 3 hypotheses for primary endpoints H_{p1}, H_{p2} and H_{p3} ; and proceed to Step 1a, otherwise, go to step 2.	
Step 1a. If $p_{s1} < \alpha$, then claim success on both hypotheses for key secondary endpoints H_{s1} and H_{s2}; otherwise, go to step 1b.
 
Step 1b. If $p_{s2} < \alpha/2$, then claim success on hypothesis for key secondary endpoint H_{s2}; otherwise, both hypotheses for key secondary endpoints H_{s1} and H_{s2} are unsuccessful

Step 2. If $p_{p2} < \alpha/2$, then claim success on two hypotheses for primary endpoints H_{p2} and H_{p3} ; and proceed to Step 2a, otherwise, go to step 3.	
Step 2a. If $p_{s1} < \alpha/2$, then claim success on both hypotheses for key secondary endpoints H_{s1} and H_{s2}; otherwise, go to step 2b.
 
Step 2b. If $p_{s2} < \alpha/4$, then claim success on hypothesis for key secondary endpoint H_{s2}; otherwise, both hypotheses for key secondary endpoints H_{s1} and H_{s2} are unsuccessful

Step 3. If $p_{p3} < \alpha/3$, then claim success on hypothesis for primary endpoint H_{p3} ; and proceed to Step 3a, otherwise, no success on all 3 hypotheses for primary endpoints H_{p1}, H_{p2} and H_{p3}	
Step 3a. If $p_{s1} < \alpha/3$, then claim success on both hypotheses for key secondary endpoints H_{s1} and H_{s2}; otherwise, go to step 3b.
 
Step 3b. If $p_{s2} < \alpha/6$, then claim success on hypothesis for key secondary endpoint H_{s2}; otherwise, both hypotheses for key secondary endpoints H_{s1} and H_{s2} are unsuccessful

$\alpha = 0.05$ for Endothermal Ablation (ETA) study.	

VenaSeal vs. Surgical Stripping Randomized Study

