7.9.1.2 Analysis of Key Secondary Endpoints

7.9.1.2.1 Hypothesis

For key secondary endpoint of return to work, the following hypothesis will be tested:

$$H_0: S_A(t) = S_C(t)$$

$$H_a: S_A(t) \neq S_C(t)$$

Where $S_A(t)$ and $S_C(t)$ are the survival functions for freedom from return to work for the VenaSeal™ system arm and ETA or surgical stripping arm, respectively.

For the other key secondary endpoint of primary target vein closure rate at 6 months, the following hypothesis will be tested:

$$H_0: S_A(t) \leq S_C(t) - 10\%$$

$$H_a: S_A(t) > S_C(t) - 10\%$$

Where $t = 6$ months, and $S_A(t)$ and $S_C(t)$ are the survival functions for freedom from vessel re-opening at 6 months in the VenaSeal™ system arm and the ETA or surgical stripping arm, respectively and -10% is the non-inferiority margin.

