7.9.1.2.4 Analysis Methods

For the return to work endpoint, a Kaplan-Meier survival estimator will be used to estimate the survival functions for both the VenaSeal™ and the control arm (i.e., ETA or Surgical Stripping). Day zero is the date of the index procedure. The censoring time is the time to study exit, the later of either the last contact date or the discontinuation date, or the time point for analysis, whichever comes first. A cumulative incidence figure will be produced to compare the two treatments. A log-rank test will be used to test whether the survival distributions differ between the treatment groups. If a patient is reported to have returned to work, but the date of return is unknown, the return date will be imputed from the date of the follow-up visit. For those who have returned to work, the median, Q1, Q3, minimum, and maximum will summarize the number of days to return to work, as well as the number who have not returned to work in each treatment arm.

The treatment effect for primary target vein closure at 6 months, one of the key secondary endpoints, is the difference in the survival curves at time t for each randomized study. A Kaplan-Meier survival estimator will be used to estimate each curve. Day zero is the date of the index procedure. The censoring time is the time to last study visit (scheduled or unscheduled), the time point for analysis, or time to exit, whichever comes first. The non-inferiority test for treatment (VenaSeal) versus control (ETA or Surgical Stripping) will be performed using the test statistic proposed in da Silva, Logan and Klein (2009)³. The Z test statistic will calculate $S_A(t) - S_C(t) + 0.10$ for the numerator where t is at 6 months and the square root of the sum of the Greenwood's variance estimators for each of $S_A(t)$ and $S_C(t)$ in the denominator.

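### Non-inferiority on closure can be claimed at one-sided 5%, a looser standard than the two-sided tests in the same scheme, and at that step its actual error is modestly above 5%

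*SAP*

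**What the plan says.** **Error rate.** SAP 6.1 and protocol 14.1 set a family-wise type I error of 0.05 for each randomized study. Neither says whether this is one- or two-sided.

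**Thresholds.** SAP 7.5 passes alpha from the primaries to the two key secondaries. If all primaries succeed and the larger key secondary p-value is below 0.05 (Step 1a), "then claim success on both hypotheses for key secondary endpoints". If only some primaries succeed, the thresholds are smaller fractions of 0.05.

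**Sidedness.** SAP 7.9.1.1.3 uses two-sided p-values for the primaries. The one-tail p-value formula printed for the Wilcoxon test in 7.9.1.1.4 sits beside a two-sided rejection rule. SAP 7.9.1.2.1 gives return to work a two-sided alternative. Closure is different: under 7.9.1.2.3 its null "will be rejected when the one-sided P-value is less than the pre-specified alpha per adjustment of multiple comparison".

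**Sizing test.** SAP 6.1.2 sizes closure with a "Likelihood Score (Farrington & Manning) test with one sided" alpha of 0.0167. It assumes 95% closure for VenaSeal, and 95.4% "and 84.8% in ETA and surgical stripping arm, respectively".

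**Analysis test.** In SAP 7.9.1.2.4, "The non-inferiority test for treatment (VenaSeal) versus control (ETA or Surgical Stripping) will be performed using the test statistic proposed in" a cited methods paper. The denominator is the square root of the two arms' summed Greenwood variances. In 7.9.1.2.1, t is 6 months "and -10% is the non-inferiority margin".

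**The concern.** At full alpha, a two-sided test at 0.05 gives a false claim in favour of VenaSeal at most 2.5% probability. The closure test has a nominal 5% in that direction. The main anatomical claim would then need less evidence than any other formal claim in the study.

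The Greenwood Z adds to this. Its variance is not restricted to the null, and with closure near 95% it is too small on average at the null boundary. The question is whether the two features together push the error past the 0.05 that the SAP promises.

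Step 1a is not a remote case. SAP 6.1.3 plans at least 90% power on each primary in the ETA study, and SAP 6.1.2 says return to work needs only 22 subjects (ETA) or 10 (stripping) for 90% power. On the plan's own assumptions, closure in the ETA study would normally be judged at 0.05.

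**Working it through.** **Inputs.** Rates, margin, 119 and 44 evaluable per arm, and 10% attrition come from SAP 6.1.2. The 108 stripping subjects come from SAP 6.1 (54 per arm; 108 × 0.9 / 2 = 48.6 evaluable). Thresholds come from SAP 7.5.

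**1. Reproducing the plan's sample size.** The Farrington-Manning formula per arm is n = [(z(1-alpha) × s0 + z(power) × s1) / (pA - pC + 0.10)]^2. Here s1^2 = pA(1-pA) + pC(1-pC), and s0^2 is the same quantity at the estimates restricted to a difference of -0.10.

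- ETA: s1 = 0.3023; restricted estimates 0.8726 and 0.9726, so s0 = 0.3713. n = [(2.127 × 0.3713 + 0.8416 × 0.3023) / 0.096]^2 = 118.3, so 119. 238 / 0.9 = 264.4, against the stated 264. Exact power at 119 is 81.9%.
- Stripping: the approximation gives 46. Exact enumeration first reaches 80% at 44 (83.7%), the plan's figure. 88 / 0.9 = 97.8, so 98.
- The unpooled formula gives only 88 and 39 per arm, so the plan was sized with the score test.

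**2. Exact error of the analysis test.** Without censoring, Greenwood's variance equals p(1-p)/n, so Z = (pA - pC + 0.10) / sqrt[pA(1-pA)/n + pC(1-pC)/n]. I summed the two binomial probabilities over all outcomes that reject, with VenaSeal exactly 10 points below control.

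| Comparison | n per arm | SAP's Z at 0.05 | Score test at 0.05 | SAP's Z at 0.025 | Score test at 0.025 |
|---|---|---|---|---|---|
| ETA, 95.4% v 85.4% | 119 | 6.03% | 4.75% | 3.2% | 2.3% |
| Stripping, 84.8% v 74.8% | 44 | 5.2% | 5.2% | 2.9% | 2.3% |
| Stripping | 49 | 5.6% | 5.2% | 2.8% | 2.6% |
| Stripping | 54 | 5.4% | 5.3% | 2.8% | 2.4% |

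At 0.0167 the SAP's Z has size 2.5% for ETA. Kaplan-Meier simulation with 10% dropout, at 0.05, gives 6.0% (ETA) and 5.4% to 5.5% (stripping).

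**3. Error across the two key secondaries.** Suppose all primaries have passed, both key secondary nulls are true and the p-values are independent. With c05 and c025 the closure sizes at 0.05 and 0.025, the family error is 1 - (1 - c025)(1 - 0.025) + (c05 - c025)(0.05 - 0.025).

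- ETA: 1 - 0.9684 × 0.975 + 0.0287 × 0.025 = 5.6%.
- Stripping (54 per arm): 1 - 0.9717 × 0.975 + 0.0252 × 0.025 = 5.3%.

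If VenaSeal truly shortens return to work, closure is in effect tested at 0.05 and the error is the 6.0% or 5.2% to 5.6% above.

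**4. What the rule accepts.** Take 119 per arm, 5 failures on ETA and 10 on VenaSeal. The difference is -5/119 = -4.20 points, with standard error 3.14 points. Z = 5.80 / 3.14 = 1.85, above 1.645, so non-inferiority is declared. The lower limit of the 90% interval is -9.4 points; that of the 95% interval is -10.4. The doubled-p rule would not accept this result.

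**The case against.** Much of the opposing case stands.

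- **One-sided entry is valid.** A correct one-sided p-value can enter Hochberg without inflating error. For ETA the score test at one-sided 0.05 has size 4.75%, so the excess needs both features. For stripping the score test itself gives about 5.2% through discreteness, so the variance choice matters little there.
- **The choice is open.** The SAP states the one-sided rule plainly and never says the family-wise 0.05 is directional. Whether non-inferiority should be shown at 5% or 2.5% is partly convention. The earlier extension study in protocol 4.1 used one-sided 2.5% with the same margin, but that is background to a different, 60-month analysis and does not bind this plan.
- **The excess is conditional.** It arises only when all primaries succeed and return to work has p below 0.05.

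A reader might also draw two stronger conclusions that the documents do not support. The first is that testing at three times the sizing level (0.05 / 0.0167) is itself a defect. SAP 6.1 says "A type I error of 0.0167 will be used in the following sample size calculations for this purpose", and every endpoint is sized at that level. Sizing at a strict step and testing at a looser one protects power. The second is that the stripping error is 7% to 8%. That needs stripping closure of 95% to 97%; SAP 6.1.2 assumes 84.8%.

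What the objection does not remove is the different evidential standard for closure, or the mismatch between the test in 6.1.2 and the test in 7.9.1.2.4.

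**Conclusion.** The concern holds in a limited form. At Step 1a the plan allows non-inferiority on closure at nominal one-sided 5%, a looser standard than any other formal claim. With the Greenwood Z, the actual error there is about 1 point over 5% for ETA and 0.2 to 0.6 point over for stripping. At lower steps it stays below 5%. The sample size is not too small, and the Hochberg procedure is not broken by the one-sided entry.

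These figures assume the SAP's control closure rates and the evaluable numbers shown. For ETA at 119 per arm the size runs from 5.3% to 8.3% as the control rate goes from 90% to 100%. The exact figures ignore censoring; the simulation with 10% dropout agrees with them. The main reason to act is the inconsistent standard; the small excess error is secondary.

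**What to change.** 1. In SAP 7.5 and 7.9.1.2.3, enter closure as twice its one-sided p-value. At full alpha this means that the lower limit of the two-sided 95% interval must exceed -10 points. State that the family-wise 0.05 is two-sided.
2. In 7.9.1.2.4, keep the Kaplan-Meier difference. SAP version 3.0 adopted it to handle censoring and unscheduled visits, and a binomial Farrington-Manning test would undo that. Either state that the Greenwood Z is slightly liberal (about 3.2% at nominal 2.5% for ETA), or add a score-type or transformed Kaplan-Meier interval for the difference as a sensitivity analysis.
3. In 6.1.2, say that the sizing used a score test at one-sided 0.0167 and explain how this relates to the analysis test.

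**Cost.** SAP wording only, with no change in sample size. The real cost is a stricter threshold at every step. Exact power for ETA at 119 per arm after doubling:

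| Step | One-sided level | Greenwood Z | Score-type test |
|---|---|---|---|
| 1a | 0.025 | 92.5% | 87.2% |
| 2a | 0.0125 | 87.9% | 78.6% |
| 3a | 0.0083 | 83.8% | 71.4% |

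Undoubled, the Greenwood Z has 95.7% at Step 1a. For stripping at 44 per arm, the doubled Greenwood Z has 90.8% at Step 1a and 85.3% at 2a. A score-type test as the primary analysis would fall below the planned 80% for ETA at Steps 2a and 3a, which is a reason to use it only as a sensitivity analysis.

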7.9.1.2.4 Analysis Methods

For the return to work endpoint, a Kaplan-Meier survival estimator will be used to estimate the survival functions for both the VenaSeal™ and the control arm (i.e., ETA or Surgical Stripping). Day zero is the date of the index procedure. The censoring time is the time to study exit, the later of either the last contact date or the discontinuation date, or the time point for analysis, whichever comes first. A cumulative incidence figure will be produced to compare the two treatments. A log-rank test will be used to test whether the survival distributions differ between the treatment groups. If a patient is reported to have returned to work, but the date of return is unknown, the return date will be imputed from the date of the follow-up visit. For those who have returned to work, the median, Q1, Q3, minimum, and maximum will summarize the number of days to return to work, as well as the number who have not returned to work in each treatment arm.

The treatment effect for primary target vein closure at 6 months, one of the key secondary endpoints, is the difference in the survival curves at time t for each randomized study. A Kaplan-Meier survival estimator will be used to estimate each curve. Day zero is the date of the index procedure. The censoring time is the time to last study visit (scheduled or unscheduled), the time point for analysis, or time to exit, whichever comes first. The non-inferiority test for treatment (VenaSeal) versus control (ETA or Surgical Stripping) will be performed using the test statistic proposed in da Silva, Logan and Klein (2009)³. The Z test statistic will calculate $S_A(t) - S_C(t) + 0.10$ for the numerator where t is at 6 months and the square root of the sum of the Greenwood's variance estimators for each of $S_A(t)$ and $S_C(t)$ in the denominator.

